June 12, 2023

Ifaa Effectiveness Evaluation on Food Security and Nutrition

NCT05825716

Clinicaltrials.gov NCT05825716

JHSPH IRB Research Plan for New Data Collection

IRB Version: 11May2023

For new data collection, new data collection plus secondary data analysis, biospecimen repositories, and data coordinating center protocols.

DO NOT DELETE ANY QUESTIONS FROM THIS TEMPLATE

PI Name: [name]

Study Title: Ifaa Effectiveness

IRB No.: 23765

PI Version No. / Date: Version 4, June 12, 2023

I. Aims of the Study:

The Ifaa Project is a USAID-funded Resilience and Food Security Activity (RFSA) that is being implemented by Catholic Relief Services (CRS) and partners in the East Hararghe Zone of the Oromia Region in Ethiopia. Ifaa targets households that are participating in Productive Safety Net Programme (PSNP) which is a social protection program administered by the Government of Ethiopia that provides food and cash assistance to vulnerable households. The Ifaa Project will deliver multi-sectoral programming in 241 kebeles (sub-districts) in nine woredas (districts) of East Hararghe Zone, however, intervention packages vary by location. The proposed effectiveness evaluation will quantify the impacts of three different intervention packages in terms of key project indicators in the areas of household food security, diet, and child nutrition.

II. Background and Rationale:

Food insecurity and child undernutrition are persistent challenges in Ethiopia. In early 2023, over 22 million Ethiopians are food insecure as a result of drought, conflict and rising food prices and the situation is expected to worsen.ⁱ Prevalence of chronic malnutrition (stunting) is estimated at 37% and prevalence of acute malnutrition (wasting) is 7% among children less than five years of age. Only 14% of children have adequate dietary diversity and 11% meet the criteria for having a minimally acceptable diet.ⁱⁱ

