We will obtain anthropometric measurements on children that are <5 years of age at baseline and endline. Mid-upper arm circumference, weight and height will be collected. Child assent will not be obtained because of the young ages; instead consent of a parent or adult household member will be requested.

g. If children are included in the study, how you will obtain permission for them to participate from their parent, legal guardian, or other legal authority (if child is in foster care or under government supervision). If any of the children are "wards of the state", additional regulatory requirements will apply:

During the consent procedure, the enumerator will inform the anthropometric measurement of a child and will get permission from his/her mother.

h. If you are seeking a waiver of informed consent or assent, the justification for this request:

No, we will not have any waiver of informed consent for this study.

i. Whether you will include a witness to the consent process and why:

No, we will not have a witness to the consent process; this is not common practice in this setting.

j. If the language is unwritten, explain how you will communicate accurate information to potential participants and whether you will use props or audio materials:

Not applicable, the language is written.

2. Identify the countries where the research will take place, and the languages that will be used for the consent process.

| Country | Consent Document(s) (Adult Consent, Parental Permission, Youth Assent, etc.) | Languages |
|----------|--|------------|
| Ethiopia | Adult Consent, parental permission | Afan Oromo |
| | | |
| | | |

C. **Study Implementation:**

1. *Describe the procedures that participants will undergo. If complex, insert a table below to help the reviewer navigate.*

Following the consent process, the enumerator will use a tablet to conduct the baseline survey. The enumerator will secure a quiet place within or nearby the participant's residence to ensure privacy. The enumerator will read each question in the tablet to the study participant and record their answer to the tablet. The enumerator will provide explanation if study participants are not able to understand a question. The same procedure will be used for the endline survey. When the interview is over, the enumerator will request to take anthropometric measurements (weight, height, arm circumference) for all children <5 years of age.

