The outcome variables of focus at the household level will be measures of food security, including 1) [Food Consumption Score](#), 2) [Household Hunger Scale](#), and 3) [Coping Strategies Index](#). At the individual level, outcome variables of focus will include 1) [Infant and Young Child Feeding Indicators](#) (in particular achievement of minimum dietary diversity); and 2) prevalence of stunting and wasting, in accordance with the [World Health Organization Child Growth Standards](#). Background information on individual (e.g. literacy, age, pregnancy status) and household characteristics (e.g. size, residence location) will also be collected so that these can be controlled for or used for disaggregation in data analysis. All outcomes will be analyzed as continuous variables and as categorical variables based on pre-determined thresholds.

A descriptive analysis of household sociodemographic characteristics and outcome measures will be performed. Continuous variables will be presented as mean (SD) and categorical variables as n (%). ANOVA tests will be conducted for baseline characteristics and primary and secondary outcomes to examine the comparability between the three and intervention groups; individual/household characteristics with significant differences between groups at baseline will be controlled for in models that estimate the effect of the interventions.

The program effect on expected primary outcome measures will be estimated using mixed-effect linear regression analysis for continuous outcomes and Generalized Estimation Equation (GEE) model for binary outcomes. In the mixed-effects models, the random effect component included indicators to control for clustering at school levels. The fixed component included the intervention group (intervention vs. control), time and an interaction term for group and time. The GEE models will be used to examine binary outcomes with longitudinal data from both enrollment and endline. These models will estimate the change in a binary outcome among members of a given intervention group from enrollment to endline, compared to the change in the same outcome in the control. The GEE models also included an interaction term between the intervention group and time (baseline/endline).

5. **Answer the following if they are relevant to your study design:**

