We anticipate maintaining identifiable data for approximately 25-30 months, during study data collection and data verification/cleaning. After data cleaning is completed, all unique identifiers will be removed from the data and only a copy of de-identified data will be maintained. If GPS coordinates are maintained, a central cluster coordinate will be used instead of specific household locations.

A. Certificate of Confidentiality:

All NIH studies include Certificate of Confidentiality (C of C) protections with the grant; the consent form must include the C of C language provided in our template. Other funders may obtain C of C protections through NIH. [<https://grants.nih.gov/policy/humansubjects/coc.htm>]

Does the study have Certificate of Confidentiality protections? Yes No

VII. Risks of the Study:

A. Describe the risks, discomforts, and inconveniences associated with the study and its procedures, including physical, psychological, emotional, social, legal, or economic risks, and the risk of a breach of confidentiality. Include risks beyond individuals to include the study population as a group and community risks. Ensure that the risks described in the consent documents are consistent with the risks outlined in the research plan.

We do not anticipate any physical, psychological, emotional, social, legal, economic or breach of confidentiality risks to the study participants. The data being collected is not sensitive. The primary inconvenience for participants is time spent to participate in the study which is anticipated to be no more than two hours over the two year study period.

B. Describe steps you will take to mitigate or minimize each of the risks described above. Include a description of your efforts to arrange for care or referral for participants who may need it.

The JHU research team will ensure the data collection team receives training in privacy and confidentiality using content developed based on guidance from the JHSPH IRB. It is anticipated that data collectors will not have access to interview data after it has been transmitted from tablets and that only a small number of study teams will maintain access to the data, thereby reducing risk of breach of confidentiality.

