Prior to and during each phase of data collection, the team will have regular calls to ensure adequate coordination and progress; in addition regular data quality monitoring and email correspondence will be used as a means of communication during data collection. Following the training of survey teams, quantitative baseline data collection will be conducted at the participants' households using Tablets/smartphones on the KOBO data platform. The baseline survey planning and logistics, and participant recruitment and data collection is planned to occur in May 2023. Following the two years of Ifaa intervention, JHU endline data collection will occur in May 2025, and will follow a similar process as baseline.

A training protocol will be designed by the JHU study team which will be delivered over a several day period to data collectors prior to each round of data collection. The training will be led by [name] and supervisors from the local data collection firm. The training elements will include an overview of the study rationale, objectives, protocol, review of the quantitative tool, interviewing techniques, field survey procedures, field organization, quality control measures and IRB protocols, to ensure safety, confidentiality, and consent procedures. Training will include content based on the JHSPH IRB Field Guide and also be specifically tailored to the questionnaire content. As part of the training, a field test will be conducted to give enumerators the opportunity to practice the consent process and interviews; following the field test modifications may be made to further tailor the questionnaire to the context (during the baseline survey only).

At each round of data collection, enumerators will be directly supervised by a team leader with experience conducting surveys. Data collection will be co-supervised by the data collection firm (using their usual practices) with additional on-the-ground support from [name] along with remote data quality monitoring managed by [name].

2. *What are the qualifications of study personnel implementing the project?*

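### Section VII.B is silent on care or referral, and no visible text makes an enumerator act on a child's low arm circumference

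*Combined protocol and SAP*

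**What the plan says.** The template question at section VII.B has two parts. It asks for steps to reduce the risks listed just above it, and then adds: "Include a description of your efforts to arrange for care or referral for participants who may need it". The answer is two sentences long. The first begins "The JHU research team will ensure the data collection team receives training in privacy and confidentiality"; the second says that few people will keep access to the data. Section VII.C follows directly, so nothing has been cut from this answer.

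On measurement, section V.B.1.f states: "We will obtain anthropometric measurements on children that are <5 years of age at baseline and endline". It continues: "Mid-upper arm circumference, weight and height will be collected". Section V.C.1 places the measurements after the interview and applies them to all children under 5 in the household. The data analysis plan in section V.C lists "prevalence of stunting and wasting" among the child outcomes.

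On what the family is told, section V.B.1.g says that during consent "the enumerator will inform the anthropometric measurement of a child and will get permission from his/her mother". That covers the fact of measurement and permission for it. It does not mention the result.

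On timing, the title block reads "Version 4, June 12, 2023", and section X.A says: "The baseline survey planning and logistics, and participant recruitment and data collection is planned to occur in May 2023". Endline is planned for May 2025.

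**The concern.** Acute malnutrition is treatable, and arm circumference can be read on the spot. If the visible plan is followed as written, an enumerator may record a low value for a young child and leave without telling anyone in the household. The template asks about care or referral for people who may need it, and the answer does not take up that part of the question.

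What is at stake is participant safety. No estimate, test or sample size depends on it.

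**Working it through.** **Text check.** These are the visible passages closest to a referral step, with what each one does.

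- Section VII.B: privacy training and data access only.
- Section V.B.1.g: the mother is told that the child will be measured and gives permission. No feedback of the result is mentioned.
- Section X.A: training covers safety, consent and content from the IRB Field Guide. The content itself is not shown.
- Section X.C: the answers on safety monitoring are N/A.
- Section X.D: human-subjects and child-protection training. Malnutrition is not mentioned.
- Section VIII.A: the evaluation itself offers participants no direct benefit.
- Table 1, Basic package: the government health extension programme, nutrition linkages for Temporary Direct Support clients, and capacity building on community management of acute malnutrition (CMAM). These are programme activities, and nothing ties them to a survey reading.
- Section III.A, footnote 3: feeding sessions for children at risk. Section III.A lists them with the enhanced interventions, so they cannot be assumed for the Basic arm.

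Several of these could receive a referred child. None makes a reading trigger a referral.

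**Scale, for illustration.** The plan gives no count of malnourished children. Its household total reproduces from sections III.A and III.B: 9 woredas × 2 kebeles × 3 clusters × 20 households = 1,080 per group, and × 3 groups = 3,240.

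Inputs:

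- Loss to follow-up of 20% (section III.B), so 3,240 × 0.80 = 2,592 households at endline.
- Children under 5 per household: 0.83 (section III.B, footnote 5, an average over all PSNP households) to 1.2 (assumed). The lower figure is probably too low, because eligibility requires a pregnancy or a child under 36 months, and such a child is still under 60 months after 24 months.
- Wasting prevalence: 7% (section II, a national figure), with 4% to 10% as an assumed range.

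Wasted children = households × children per household × prevalence.

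- Endline at 7%: 2,592 × 0.83 × 0.07 = 151; 2,592 × 1.0 × 0.07 = 181; 2,592 × 1.2 × 0.07 = 218.
- Endline at 4% to 10%: 2,592 × 0.83 × 0.04 = 86; 2,592 × 1.2 × 0.10 = 311.
- Baseline at 7%: 3,240 × 0.83 × 0.07 = 188; 3,240 × 1.2 × 0.07 = 272.

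**Time cost at endline.** Assume 3 to 10 minutes per flagged child, and take the wasted count as a stand-in for the flagged count.

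- Low: 86 × 3/60 = 4.3 hours. High: 311 × 10/60 = 51.8 hours.
- Interview time at 40 to 50 minutes (section V.C.2): 2,592 × 40/60 = 1,728 hours; 2,592 × 50/60 = 2,160 hours.
- Share: 4.3/2,160 = 0.2%; 51.8/1,728 = 3.0%.

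**The case against.** - **Unseen text.** The consent pages, the training content and the part of section X.A after the question on staff qualifications are not available. The consent script is a natural place to promise feedback of a result. This stands. A reader might infer that the study has no referral procedure, but the documents support only the narrower statement that VII.B does not mention one and no visible text supplies one.
- **A narrower reading of VII.B.** The question opens with the risks just described, section VII.A names none beyond time, and malnutrition already present is not caused by the survey. That reading is possible. However, the question's last clause speaks of participants who may need care, without limiting the need to study-related harm.
- **What the field team can know.** Wasting is an outcome derived against WHO growth standards, and nothing says that z-scores are computed during the visit. This stands: only arm circumference offers an immediate signal, and the documents give no cut-off for it.
- **The count.** A reader might infer that some 200 children per round would be flagged and left without help. The documents do not support that. The figure comes from a national wasting prevalence, and an arm-circumference rule may flag more or fewer children and would miss wasted children above its cut-off.
- **Urgency.** Participants are already programme beneficiaries, with health extension and CMAM support in the Basic package. This lowers the priority but does not supply the missing link.

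**Conclusion.** The point holds in limited form. The VII.B answer is fully visible and leaves the care-or-referral part of its question unaddressed. No visible text requires an enumerator to tell the caregiver about, or refer, a child under 5 whose arm circumference indicates acute malnutrition.

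The illustrative scale is 151 to 218 wasted children at endline, or 86 to 311 over the wider assumed prevalence. It rests on 7% (or 4% to 10%) wasting, 0.83 to 1.2 children under 5 per household and 20% loss. The conclusion does not depend on the exact count.

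A reader might also infer that both rounds can still be changed. The dates do not support that: this version is dated after the month planned for baseline, so only the endline is certainly open.

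Priority: optional, below findings that affect inference.

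**What to change.** Add one procedure to sections VII.B and V.C.1, identical in all arms, for the May 2025 endline, and for baseline only if it is still under way:

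1. After measurement, the tablet compares the recorded arm circumference with the national CMAM criterion. The team inserts the value and age range, which the documents do not give.
2. Before leaving, the enumerator tells the caregiver the result and gives a written referral to the government health extension service. That service is in the Basic package and so common to all arms. The team should confirm that it can provide or arrange treatment.
3. Flagged and notified are recorded for each child.

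Add matching consent wording, and submit the change with the endline questionnaire modification already foreseen in section V.C.1. If the consent or training text already contains the step, a cross-reference in VII.B is enough.

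The cost is a printed slip, a short training item, some wording, and about 4 to 52 enumerator-hours at endline (0.2% to 3.0% of interview time). With one flagged child, a 40 to 50 minute visit becomes 43 to 60 minutes. This keeps to the stated hour only if the 40 to 50 minutes already includes measurement.

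At endline, referral follows measurement and cannot affect the outcomes. If also done at baseline, it could change endline wasting by an unknown amount. The change might differ by arm, because the feeding sessions belong to the enhanced package. Recording the flag lets this be reported by arm but does not remove it.

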The JHU PI and Co-Is will have oversight over the data collection process. As the data will be collected through an online platform, JHU will have full access to the data entry and management platform. JHU team member [name] is based in Ethiopia and will be responsible for interviewer training and management of the data collection process. [name] and [name] have calls several times a week and regularly communicate via email. [name] does not have site visits planned explicitly for this study, however, she regularly travels to Ethiopia for the Ifaa Project with her travel scheduled planned around maximizing the utility of visits across multiple ongoing Ifaa studies.

B. Protocol Compliance and Recordkeeping:

Describe how you plan to ensure that the study team follows the protocol and properly records and stores study data collection forms, IRB regulatory correspondence, and other study documentation (for assistance, contact: [contact]).

Please provide information about study oversight to ensure compliance with IRB approval and regulatory and institutional requirements. If the study team does not follow study procedure, what is your plan for reporting protocol non-compliance?

Any reported breach of data protocols and non-compliance with IRB will be immediately addressed by the JHU research team and corrected or the individual study team member removed from the study.

C. Safety Monitoring:

1. *Describe how participant safety will be monitored as the study progresses, by whom, and how often. Will there be a medical monitor on site? If yes, who will serve in that role and what is that person's specific charge?*

[N/A]

2. *If a Data Safety Monitoring Board (DSMB), or equivalent will be established, describe the following:*

- a. *The DSMB membership, affiliation and expertise.*

[N/A]

- b. *The charge or charter to the DSMB.*

[N/A]

- c. *Plans for providing DSMB reports to the IRB.*

[N/A]

3. *Describe plans for interim analysis and stopping rules, if any.*

[N/A]

D. Reporting Unanticipated Problems/Adverse Events (AEs) to the IRB (all studies must complete this section):

NOTE: The IRB does not require PROMPT reporting of all AEs, only those that are unanticipated, pose risk of harm to participants or others, and are related to the study. Anticipated AEs may be reported with the Continuing Review/Progress Report.

Describe your plan for reporting to the JHSPH IRB, local IRBs, and (if applicable) to the sponsor. Include your plan for government-mandated reporting of child abuse or illegal activity.

The data teams will be trained on the JHU human subjects research guidelines, confidentiality, safety and protection. They will also receive training on appropriate child protection guidelines required by CRS Ethiopia.

E. Other IRBs/Ethics Review Boards:

If other IRBs will review the research, provide the name of each IRB/ethics review board and its Federal Wide Assurance number, if it has one (available on [[OHRP's Website](#)]). For federally funded studies, subrecipients MUST have a Federal Wide Assurance (FWA) number from the OHRP. The IRB overseeing the subrecipient should be registered with the OHRP. The JHSPH IRB will not have oversight responsibility for international subrecipients, and generally will not oversee data collection at external U.S. institutions. Please contact the [[JHSPH IRB Office](#)] with questions.

| Non-JHSPH IRB/REC | FWA Number |
|--|------------|
| Oromia Regional Administration (local authority) | 18852 |
| Ethiopia Public Health Association | 19561 |

F. “Engaged” in Human Subjects Research:

For studies that involve collaboration with non-JHSPH institutions, complete the chart below by describing the collaboration and the roles and responsibilities of each partner, including the JHSPH investigator. This information helps us determine what IRB oversight is required for each party. Complete the chart for all multi-collaborator studies.

Insert collaborator names and FWA numbers, if available. Note who will be “engaged” in human subjects research by filling in the following table:

| | JHSPH | Local Data Collection Firm | CRS |
|---|----------|----------------------------|----------|
| For federally funded studies, collaborators' FWA | 00000287 | | 00027851 |
| Primary Grant/Contract Recipient | | | X |
| Grant/Contract Subrecipient | X | X | |
| Hiring Data Collectors | | X | X |
| Training Data Collectors | X | X | |
| Obtaining Informed Consent and/or Identifiable Data | | X | |
| Accessing/Analyzing Identifiable Data | X | | |
| Overseeing storage, access and use of biospecimens | N/A | N/A | N/A |

COMPLETE THE FOLLOWING SECTIONS WHEN RELEVANT TO YOUR STUDY: none are relevant

REFERENCES

ⁱ <https://reports.unocha.org/en/country/ethiopia/card/1THC27CGy6/>

